9 STATISTICAL CONSIDERATIONS

The sections of the Statistical Considerations describe the statistical methods to be used to analyze the efficacy and safety. These methods may be revised and updated due to reasons such as regulatory requirements or need for further clarifications. The final analysis plan will be documented in a formal statistical analysis plan (SAP) that must be finalized before database lock. The SAP will include details on how variables will be derived, how missing data will be handled, and how censoring procedures will be applied to time to event related variables as well as the details on statistical methods to be used for safety and efficacy analyses. The final clinical study report will discuss deviations from the SAP, if any.

9.1 SAMPLE SIZE AND POWER

9.2 GENERAL ANALYSIS CONVENTION

This is an open-label, Phase 2, study of the PI3K delta inhibitor umbralisib in combination with ublituximab. This trial is designed to evaluate the overall response rate (CR + PR), as well as duration of response (DOR), complete response (CR), and progression-free survival (PFS) in treatment naïve follicular lymphoma and small lymphocytic lymphoma subjects. Assessment of lymphoma response (CR, PR or SD) and disease progression will be evaluated as outlined in the schedule of assessments (Section 5), according to the Revised Response Criteria for Malignant Lymphoma (Cheson et al. 2007). Subjects who progress according to the corresponding criteria will receive no further treatment. Subjects who respond to the treatment (i.e., CR, PR or SD) may remain on trial.

Safety will be examined on an ongoing basis while the study is being conducted. Toxicity will be assessed utilizing the National Cancer Institute Common Terminology Criteria for Adverse Events (NCI CTCAE) v4.0 (<http://evs.nci.nih.gov/ftp1/CTCAE>).

Unless otherwise stated, all analyses will be performed using SAS Version 9.4 or higher and all hypothesis tests will be conducted at a two-sided significance level of 0.05.

In general, summary tabulations will display the number of observations, mean, standard deviation, median, minimum, maximum, and appropriate percentiles for continuous variables, and the number and percentage by category for categorical data. Summaries will be presented. The data listings will include all available efficacy and safety data.

9.3 STUDY POPULATIONS

Two study populations, intent-to-treat (ITT) and safety populations, are pre-defined for this study. The ITT population will include all enrolled subjects who provide some efficacy assessments and the safety population will include all subjects who take at least one dose of study medication. The efficacy analyses will be based on ITT population and the safety analyses will be based on the safety population.

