4.3 REGISTRATION AND ENROLLMENT

Prior to participation, subjects must willingly consent to the study after being informed of the procedures to be followed, the experimental nature of the treatment, potential benefits, alternatives, side-effects, risks and discomforts. Only eligible subjects will be enrolled onto the study.

Investigators will use an interactive web response system (IWRS) to register and enroll subjects to study UTX-TGR-203. Upon entering subject information into the IWRS, investigators will receive a unique subject identifier. This confirmation must be received by the site prior to dispensing study drug to the participant. Further details about the subject registration process using the IWRS system will be outlined in the Study Manual.

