5 STUDY ASSESSMENTS AND TREATMENT SCHEDULE

The table below lists all of the required assessments that should be performed at each study visit.

Cycle = 28 days	Screen	Cycle 1				Cycles 2-6					> Cycle 6		End of study ¹	LTFU
						C2	C3	C4	C5	C6	C9, 12, 18 and 24			
Procedure\Days	-28-1	D1²	D8	D15								Day 1	Day 1	
Medical history	X													
ECOG Performance Status³	X	X				X	X	X	X	X		X		X
Physical examination³	X	X	X	X	X	X	X	X	X	X		X		X
Vital signs (pulse, BP, temp, weight, resp)	X	X	X	X	X	X	X	X	X	X		X		X
BM Biopsy/aspirate⁴	X													
12-lead EKG	X													
Tumor evaluation⁵	X ⁵					X ⁵			X ⁵		X ⁵			X ⁵
FLIPI Staging⁶	X													
Serology: HCV, HBV, CMV⁷	X													
CMV Surveillance⁸						X			X		X			
Hematology (CBC including 5-part differential and platelets)⁹	X	X	X	X	X	X	X	X	X	X		X		
Serum Chemistry¹⁰	X	X	X	X	X	X	X	X	X	X		X		X
Cholesterol, LDL, HDL & Triglycerides¹¹	X	X				X	X	X	X	X		X		X
PT/INR	X													
Serum Pregnancy Test¹²	X													
Urine Pregnancy Test	X					X		X		X		X		
Core needle biopsy (optional)¹³	X			X										
Lymphocyte subsets¹⁵		X				X	X	X	X	X		X		X
PK Sampling (all pre-dose)¹⁶		X			X	X	X	X	X	X				
Concomitant Medications	X	X	X	X	X	X	X	X	X	X		X		X
AE Evaluation	X	X	X	X	X	X	X	X	X	X		X		X
Ublituximab		X	X	X	X	X	X	X	X	X		X ¹⁷		
Umbralisib (TGR-1202)			Administered orally daily with food through Cycle 24 ¹⁸											

¹ All subjects should undergo the end-of-study assessments listed within 30 days after treatment ends.

² Cycle 1/Day 1 procedures are all pre-dose study drug.

³ The screening physical examination, ECOG PS, cholesterol, LDL, HDL & triglycerides must be done \leq 7 days prior to initiation of treatment. However, if these initial examinations are obtained within 72 hours of Cycle 1 Day 1 they do not have to be repeated. Include assessment of B-symptoms. C1 (Day 8 & 15) and Cycle 2 (Day 1) physical exams have a \pm 3 day window, and a \pm 7 days for all visits after Cycle 2.

⁴ Subjects should have a bone marrow biopsy and/or aspirate within 90 days prior to Day 1 of Cycle 1 according to standard of care guidelines. Bone marrow biopsy and/or aspirate should also be obtained to confirm a CR. Bone marrow biopsy and aspirates should include FISH, flow cytometry and cytogenetics.

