⁵ Baseline scans should be completed within 30 days prior to Day 1 of Cycle 1. All tumor evaluations after baseline have a +/- 14 day window. Radiology assessment includes a contrast enhanced CT scan of chest, abdomen, and pelvis (and neck as clinically warranted). If iodinated contrast is contraindicated, a non-contrast chest CT coupled with a gadolinium-enhanced MRI of the abdomen/pelvis (and neck as clinically warranted) is an acceptable substitute. PET using fluorodeoxyglucose (FDG) should be done at screening for all subjects then within 14 days of Cycle 6 and to confirm potential CR. Tumor evaluation should occur within 14 days of Day 1 of Cycles 3, 6, and 12, and approximately every 6 cycles thereafter through cycle 24. During LTFU, assessments should occur approximately every 12 months.

⁶ Lymphoma staging should be captured (see Appendix E) at baseline.

⁷ Serum virology to include HBsAg, HBc antibody, HCV antibody and CMV IgG and IgM. If HBc antibody, HCV antibody or CMV IgM is positive, subjects must be evaluated for the presence of active HBV, HCV or CMV by DNA(PCR). Serum virology to include HBsAg, HBc antibody, HCV antibody and CMV.

- ⁸ CMV only should be checked by PCR approximately every 3 cycles, as part of the subject's scheduled visit. If subject is CMV positive, stop therapy and provide supportive care per investigator discretion. CMV surveillance should discontinue 30 days after last dose of umbralisib.
- ⁹ The screening hematology must be done \leq 7 days prior to initiation of treatment. However, if these initial examinations are obtained within 72 hours of Cycle 1 Day 1 they do not have to be repeated. C1 (Day 8 & 15) and Cycle 2 (day 1), laboratory assessments have a \pm 3 day window, and a \pm 7 days for all visits after Cycle 2. Hematological parameters include the following laboratory tests: complete blood count consisting of hmeatocrit, hemoglobin, total white blood count (WBC) with 5-part differential, and platelet count.

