8.4 DEFINITIONS OF TUMOR RESPONSE AND PROGRESSION

Evaluable for objective response. Only those subjects who have had a pre-treatment baseline efficacy evaluation and at least one post-treatment efficacy evaluation will be considered evaluable for response. These subjects will have their response classified according to the definitions stated below.

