8.6 EVALUATION OF BEST OVERALL RESPONSE

The best overall response is the best response recorded from the start of the treatment until disease progression/recurrence (taking as reference for progressive disease the smallest measurements recorded since the treatment started). The subject's best response assignment will depend on the achievement of both measurement and confirmation criteria as per the NHL established criteria used in this study (See Appendix A).

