9.7 EFFICACY ANALYSES

Two populations will be used in the efficacy analyses, Intent-to-Treat (ITT) and Per Protocol (PP) populations. The ITT population will include all safety population who provide efficacy assessment, and PP population will include all ITT population without major protocol violations.

The efficacy endpoints will include:

- Overall response rate (ORR)
- Complete response (CR)
- Duration of Response (DoR)
- Progression-free Survival (PFS)

These variables will be analyzed/summarized based on the ITT population as well as the PP population as appropriate. The percentages of CR, CR+PR, and CR+PR+SD will be presented, as will the median duration of response. The lower bound of these percentages will be presented using the Clopper-Pearson Exact method to estimate the 95% confidence interval.

Additional analyses may also be performed as appropriate

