9.8 MISSING VALUE HANDLING PROCEDURES

In general, other than for partial dates, missing data will not be imputed and will be treated as missing. The algorithms for imputation of partial dates may vary depending upon the parameter.

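### Sections 9.3 and 9.7 build the ITT set from different bases, and both make it depend on an undefined efficacy assessment, so the primary ORR denominator is not fixed

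*Combined protocol and SAP*

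**What the plan says.** Section 9.3 pre-defines an ITT and a safety population, bases efficacy on ITT and states: "The ITT population will include all enrolled subjects who provide some efficacy assessments". Its safety population is everyone who took at least one dose. Section 9.7 defines ITT again: "The ITT population will include all safety population who provide efficacy assessment". It also adds a per-protocol set that 9.3 does not list.

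Other sections bear on the same question:

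- Section 8.4 describes a further group: "Only those subjects who have had a pre-treatment baseline efficacy evaluation and at least one post-treatment efficacy evaluation will be considered evaluable for response". It does not connect that group to ITT or to the ORR denominator.
- Section 8.6: "The best overall response is the best response recorded from the start of the treatment until disease progression/recurrence".
- Section 9.8: apart from partial dates, and in general, "missing data will not be imputed and will be treated as missing".
- Section 9.9.1 defines ORR as a percentage of subjects and does not name the analysis set.
- Section 9 leaves variable derivation, missing data and censoring to a formal SAP, to be finalized before database lock.

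**The concern.** The study has no control arm and ORR is its primary endpoint, so the denominator directly sets the headline rate and its lower confidence limit. The plan gives two bases for that denominator, enrolled and dosed. It also attaches to both a condition that depends on what happens after enrollment.

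The subjects at risk are those treated but never assessed after baseline, for example after early death, withdrawal of consent or loss to follow-up. Such subjects cannot be recorded responders. If the condition removes them, the reported rates rise without any additional response. PFS counts death from any cause, so leaving out an early death also removes a PFS event.

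**Working it through.** **No stated figure to reproduce.** The text available gives no null or target ORR and no sample-size calculation (Section 9.1 shows a heading only, which is not held against the plan). The check compares readings of the definitions.

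**Who is exposed.** Section 5, footnote 5: "Tumor evaluation should occur within 14 days of Day 1 of Cycles 3, 6, and 12". With 28-day cycles, Cycle 3 Day 1 is day 1 + 2 × 28 = 57, and the ±14-day window runs from day 43 to day 71. A subject lost before then may have no post-baseline assessment.

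**Reading A: a post-baseline assessment is required.** ITT then behaves like the 8.4 evaluable set. Let N be the number treated, r the recorded responders and k the treated subjects never assessed after baseline. The rate is r/(N − k) instead of r/N, and r/(N − k) ≥ r/N always.

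Inputs: N = 50 (up to 50 enrolled, Section 4.1; all taken as treated) and Clopper-Pearson 95% limits (Section 9.7). The values r = 40 and k are assumptions.

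| k | ORR | Exact 95% lower limit |
|---|---|---|
| 0 | 40/50 = 80.0% | 66.3% |
| 1 | 40/49 = 81.6% | 68.0% |
| 2 | 40/48 = 83.3% | 69.8% |
| 3 | 40/47 = 85.1% | 71.7% |
| 5 (extreme) | 40/45 = 88.9% | 75.9% |

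Other rates at k = 2, with assumed counts: CR 20/50 = 40.0% becomes 20/48 = 41.7%; CR+PR+SD 43/50 = 86.0% becomes 43/48 = 89.6%.

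The upward direction is relative to recorded response. The true response of the k unassessed subjects is unknown, so the all-treated rate lies between r/N and (r + k)/N. At k = 2 that is 40/50 = 80.0% to 42/50 = 84.0%, so 83.3% could be 3.3 points too high or 0.7 points too low. At k = 5 it is 80.0% to 45/50 = 90.0%, so 88.9% could be 8.9 points too high or 1.1 points too low.

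**Reading B: the baseline scan counts.** The unassessed treated subjects stay in the set. Under 9.9.1 the natural arithmetic keeps them in the denominator and out of the numerator, but 9.8 leaves this unstated. Sections 9.3 and 9.7 now differ only for a subject enrolled but never dosed. Such a subject can exist, because Section 4.3 says of the enrollment identifier: "This confirmation must be received by the site prior to dispensing study drug to the participant".

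**Both readings on one data set (assumed).** Take 50 enrolled, 1 never dosed, 2 of the 49 treated never assessed after baseline, and 39 responders. The first two rows hold only if unassessed subjects who stay in the set are counted as non-responders.

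| Set | ORR | Exact 95% lower limit |
|---|---|---|
| 9.3, baseline counts | 39/50 = 78.0% | 64.0% |
| 9.7, baseline counts | 39/49 = 79.6% | 65.7% |
| Post-baseline required | 39/47 = 83.0% | 69.2% |

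**The case against.** The strongest reply is that the protocol's own vocabulary favors Reading B. Section 8.4 describes the baseline examination as an efficacy evaluation and says post-treatment explicitly when it means that; 9.3 and 9.7 do not. Baseline imaging is scheduled for every subject. On this view the 9.7 set is essentially everyone treated, a subject with no recorded CR or PR has simply not achieved one, and a ban on imputation does not remove anyone from a denominator. This stands as a reasonable reading, and probably the natural one, but the text does not compel it: neither ITT sentence defines the assessment, and a condition that a scheduled baseline scan nearly always meets would do little work.

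Second, k may be small. Section 5, footnote 1, says "All subjects should undergo the end-of-study assessments listed within 30 days after treatment ends", and Sections 4.1, 4.5 and 8 keep subjects who stop for reasons other than progression in follow-up. That stands too. Such follow-up should recover many early stoppers, though not reliably those who die, withdraw consent or are lost. The Phase I discontinuation figure in Section 1.2 (6/81, 7%, for adverse events) does not estimate k, because such stops stay in follow-up here.

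Third, Section 9 defers derivations and missing data to an SAP. That could supply the missing non-responder rule. It does not remove two conflicting definitions that 9.3 calls pre-defined.

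A reader might go further and infer that the plan does exclude unassessed subjects, or that its ORR will be inflated. The documents do not support either: exclusion depends on Reading A, and its effect depends on an unknown k.

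**Conclusion.** The concern holds in a limited form. It is established that 9.3 and 9.7 define the primary efficacy set from different bases, that both make it conditional on an efficacy assessment that is not defined, and that no sentence in the text says how a treated subject with no post-baseline assessment is counted. Confidence in this is high.

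Omission of treated subjects, and the rise in recorded rates that follows, is possible rather than shown. It requires Reading A and k of at least 1. At an assumed 40 responders among 50 treated, k = 2 would add 3.3 points to ORR and 3.5 points to the exact lower limit; k = 0 adds nothing. The effect on PFS likewise arises only under Reading A. No changed trial decision can be shown, because no ORR threshold is visible. The point should be fixed before database lock, since in an open-label study a denominator chosen after responses are known is open to challenge.

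**What to change.** - **Sections 9.3 and 9.7:** use one identical primary efficacy population, all subjects who received at least one dose of study drug, with no efficacy-assessment condition. Name it in 9.9.1 as the ORR denominator. An all-enrolled set would also reconcile the sections; the all-dosed set matches the existing safety population.
- **Section 9.8:** state that a subject with no post-baseline response assessment counts as not meeting ORR, CR or CR+PR+SD, as an explicit exception to the general missing-data rule.
- **PFS:** keep all treated subjects, with early deaths as events.
- **Sensitivity analyses:** keep the 8.4 evaluable set and the per-protocol set under those labels, and report the number of unassessed subjects with reasons.

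The cost is protocol and SAP wording before database lock, with no new data or procedures. The reported ORR may be slightly lower than under the restrictive reading.

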9.4 SUBJECT DEMOGRAPHICS AND BASELINE CHARACTERISTICS

Demographics and baseline characteristics will be summarized using descriptive statistics for continuous variables, and frequencies and percentages for categorical variables.

9.5 MEDICAL HISTORY

Medical history will be captured at the Screening visit. Medical history will be coded using MedDRA and will be summarized by MedDRA system organ class and preferred term for the Safety population.

9.6 EXTENT OF EXPOSURE

The dose (mg) of study drugs administered, the total number of study drug doses, and the duration of treatment (number of study cycles) will be summarized with descriptive statistics. The number and percentage of subjects whose dose is modified at any time will be summarized by each type of modification at a cycle level and overall. The proportion of subjects completing each cycle of treatment will be summarized.

9.7 EFFICACY ANALYSES

Two populations will be used in the efficacy analyses, Intent-to-Treat (ITT) and Per Protocol (PP) populations. The ITT population will include all safety population who provide efficacy assessment, and PP population will include all ITT population without major protocol violations.

The efficacy endpoints will include:

- Overall response rate (ORR)
- Complete response (CR)
- Duration of Response (DoR)
- Progression-free Survival (PFS)

These variables will be analyzed/summarized based on the ITT population as well as the PP population as appropriate. The percentages of CR, CR+PR, and CR+PR+SD will be presented, as will the median duration of response. The lower bound of these percentages will be presented using the Clopper-Pearson Exact method to estimate the 95% confidence interval.

Additional analyses may also be performed as appropriate

9.8 MISSING VALUE HANDLING PROCEDURES

In general, other than for partial dates, missing data will not be imputed and will be treated as missing. The algorithms for imputation of partial dates may vary depending upon the parameter.

9.9 STATISTICAL ANALYSES

9.9.1 PRIMARY EFFICACY VARIABLE - ORR

Overall Response Rate (ORR) will be determined per the Revised Response Criteria for Malignant Lymphoma (Cheson et al. 2007). Overall Response Rate (ORR), is defined as percent of subjects who achieve CR or PR. We will estimate 95% confidence intervals for the response rates. These will be followed by additional logistic regression analyses model to adjust for demographic and baseline parameters.

9.9.2 SECONDARY EFFICACY OUTCOMES

Secondary efficacy outcomes will include:

- Progression-free Survival (PFS), Complete Response (CR) and Duration of Response (DOR)

9.9.2.1 PROGRESSION-FREE SURVIVAL

Progression-free survival (PFS) is defined as the interval from Cycle 1/Day 1 to the earlier of the first documentation of definitive disease progression or death from any cause. PFS will be presented using the Kaplan-Meier method. Median time to event and the 95% confidence interval of the median times will be presented, if estimable. Median time to event will be tested against the null hypothesis value using a one-sample (one-sided) log-rank test.

Hypothesis testing for pairwise comparison will be performed using a log rank test via SAS Lifetest procedures. The median duration of PFS and the proportion of subjects alive and progression-free at 6, 12, and 18 months will be estimated using the Kaplan-Meier method. For each estimate, a 95% confidence interval will be reported.

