13.4 Study Monitoring, Auditing, and Inspecting.....	71
13.5 Quality Assurance and Quality Control	71
13.6 Disclosure and Publication Policy.....	72
14 REFERENCES	73
15 APPENDIX A - ECOG Performance Status Scale.....	75
16 APPENDIX B - Contraception Guidelines and Pregnancy	76
17 APPENDIX C - New York Heart Association Classifications.....	78
18 APPENDIX D - International Working Group Revised Response Criteria for Malignant Lymphoma (Cheson et al. 2007)	79
19 APPENDIX E - Follicular Lymphoma Staging and Follicular Lymphoma International Prognostic Index (FLIPI)	84
20 Appendix F - Hepatitis B Serologic Test Results	85

SUMMARY OF CHANGES

Version 1.1 (Dated 26 April 2018) of this Protocol is the first amendment to this clinical trial and contains the following modifications:

- T-cell Lymphocyte Subsets will be analyzed by the Sponsor designated central laboratory instead of the site's local laboratory (Section 5.1.2.1)
- Updated guidance for prophylaxis treatment with pneumocystis jiroveci pneumonia (PCP) and antiviral therapy (Section 6.2.1)

Version 2.0 (Dated 20 December 2018) of this Protocol is the second amendment to this clinical trial and contains the following modifications:

- The term "patient" was replaced with "subject" throughout;
- Administrative and editorial changes;
- Two safety run-in cohorts of 3 - 6 subjects each were added at a dose of 600 mg and 800 mg umbralisib to evaluate for key immune mediated toxicities. In the absence of unacceptable toxicity, enrollment will proceed with all subjects receiving 800 mg umbralisib.
- Inclusion Criteria
 - Subjects are now required to have a need for systemic therapy prior to enrollment;
 - Statement added to bilirubin noting exception of Gilbert's Disease and Autoimmune Hemolytic Anemia;
 - Calculated Creatinine Clearance utilizing the Modified Cockcroft-Gault Formula and IBM;
- Exclusion Criteria
 - The exclusion of prior cancer therapy was clarified to prior "systemic" cancer therapy;
 - Updated exclusionary criteria for hepatitis and CMV screening criteria for clarity;
 - Updated reference to note appendix F not D;
 - Added parameters for corticosteroids during screening;
- Schedule of Assessments and Treatment (Section 5.0)
 - Update response assessment criteria. Clarified assessments should be within 14 days of Day 1 of Cycles 3, 6, and 12, and then every 6 months until cycle 24. After cycle 24, response assessments should occur at least every 12 months.

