Study Objectives	
PRIMARY OBJECTIVE
 
 • To assess the overall response rate (ORR) in subjects with treatment naïve follicular lymphoma (FL) and small lymphocytic lymphoma (SLL) treated with umbralisib in combination with ublituximab. 
SECONDARY OBJECTIVES
 
 • To evaluate the safety of umbralisib in combination with ublituximab. • To assess the duration of response (DOR), Complete Response (CR) and progression-free survival (PFS) in subjects with treatment naïve FL and SLL treated with umbralisib + ublituximab. 
[REDACTED]

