4 STUDY DESIGN

4.1 OVERVIEW OF STUDY DESIGN

This is a Phase 2, open-label study of umbralisib, a PI3K delta inhibitor, administered in combination with ublituximab, a glycoengineered anti-CD20 mAb, to subjects with treatment naïve Follicular Lymphoma (FL) or Small Lymphocytic Lymphoma (SLL).

Daily doses of oral umbralisib will be administered for a duration of 24 cycles (approximately 24 months), in the absence of disease progression, unacceptable toxicity, or withdrawal from treatment. Two safety run-in cohorts of 3 - 6 subjects each at a dose of 600 mg and 800 mg umbralisib will first be enrolled to evaluate for key immune mediated toxicities. In the absence of unacceptable toxicity, enrollment will proceed with all subjects receiving 800 mg umbralisib. A fixed dose of 900 mg of ublituximab will be administered on Days 1, 8, and 15 in Cycle 1 and Day 1 of Cycles 2-6, Cycle 9 and 12. Ublituximab will be administered through Cycle 12. Treatment cycles are 28 days.

PET scans must be done at screening, within 14 days prior to Cycle 6 Day 1, and to confirm CR (if applicable). During the study period, all subjects will be evaluated for response by CT (if contrast CT is contraindicated MRI with a non-contrast CT Chest should be completed) within 14 days of Day 1 of Cycles 3, 6, and 12. After Cycle 12, subjects should be evaluated for response by CT (if contrast CT is contraindicated MRI with a non-contrast CT should be completed), approximately every 6 cycles through cycle 24, unless clinically indicated sooner (at the discretion of the treating physician).

After 24 cycles (approximately 24 months) of treatment, subjects will discontinue study medication and be followed for progression-free survival. Subjects who discontinue study drugs will have an End of Treatment visit within 30 days from the last dose of study drug. After cycle 24, subjects should have response assessment at least every 12 months or more frequently as medically indicated.

Subjects who discontinue from study treatment (for reasons other than progressive disease or completion of therapy), will have an End of Treatment visit within 30 days from the last dose of study drug. Follow for PFS as below:

- Months 1-24 approximately every 6 months
- Months 25 and beyond at least every year

Safety will be evaluated continuously throughout the study.

Up to 50 subjects are expected to be enrolled in this study.

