4.2 SAFETY RUN-IN

A 3 + 3 approach will be utilized to evaluate safety during the safety run-in phase. Three subjects will first be treated at 600 mg umbralisib in combination with ublituximab for 1 cycle (28 days). If 1/3 subjects experience an unacceptable toxicity (defined below), 3 additional subjects will be enrolled at the same dose level. If >1/6 subjects at 600 mg experience an unacceptable toxicity, it

will be deemed to exceed the MTD and enrollment to the study will stop. If $\leq 1/6$ subjects experience an unacceptable toxicity at 600 mg, then 3 subjects will be enrolled to receive 800 mg umbralisib in combination with ublituximab for 1 cycle (28 days). If $1/3$ subjects experience an unacceptable toxicity, 3 additional subjects will be enrolled at the same dose level. If $>1/6$ subjects at 800 mg experience an unacceptable toxicity, it will be deemed to exceed the MTD and enrollment to the remainder of the study will proceed at 600 mg umbralisib. If $\leq 1/6$ subjects experience an unacceptable toxicity at 800 mg, then enrollment will proceed for the remainder of the study at 800 mg umbralisib.

An unacceptable toxicity will be defined as the occurrence of transaminitis, colitis, pneumonitis, or rash during Cycle 1 that is:

- Grade ≥ 3 and persists for >7 days without resolution despite supportive care; or
- Any grade treatment emergent toxicity that results in treatment discontinuation.

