9.9.2.2 CR RATE

CR rate is defined as the percent of subjects who achieve a CR. CR rate will be analyzed via chi square test. The 95% confidence intervals for the response rates as well as for the differences of the complete

response rate will be presented. Additional logistic analyses model may be used to assess the impact of demographic and baseline parameters.

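### Sections 9.9.2.1 and 9.9.2.2 prescribe two-group inference for PFS and CR rate in a study of one open-label regimen, and the visible text names neither the groups nor a reference CR rate

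*Combined protocol and SAP*

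**What the plan says.** **PFS (9.9.2.1).** The section asks for Kaplan-Meier estimates with 95% intervals and a one-sided, one-sample log-rank test against a null value. It then adds, as a separate instruction: "Hypothesis testing for pairwise comparison will be performed using a log rank test via SAS Lifetest procedures".

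**CR rate (9.9.2.2).** "CR rate will be analyzed via chi square test". Confidence intervals are to be given for the response rates, "as well as for the differences of the complete" response rate.

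**Level of testing (9.2).** Unless otherwise stated, "all hypothesis tests will be conducted at a two-sided significance level of 0.05".

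**Objective (synopsis, repeated in substance in 2.1).** "To assess the duration of response (DOR), Complete Response (CR) and progression-free survival (PFS) in subjects with treatment naïve FL and SLL". Both histologies are named together, and no contrast between them is stated.

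**Design (synopsis, 4.1, 4.2).** All subjects receive umbralisib with ublituximab, and up to 50 are to be enrolled. The only variation in assigned treatment is the umbralisib dose around the safety run-in. After the run-in, "In the absence of unacceptable toxicity, enrollment will proceed with all subjects receiving 800 mg umbralisib". If the 800 mg cohort exceeds the toxicity limit, "enrollment to the remainder of the study will proceed at 600 mg umbralisib". Section 4.3 describes registration through a web system but no allocation between arms.

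**The concern.** A pairwise log-rank test compares the survival curves of at least two groups, and an interval for a difference in CR rates needs two rates. A chi-square test can be run on one group, but only against a stated reference proportion. The visible plan supplies none of these. The pairwise sentence cannot be read as restating the one-sample test, because it follows that test as a further instruction with its own software procedure.

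An analyst who followed the text would have to choose the groups outside the visible protocol and then test them at the general two-sided 0.05 level. Responses are reviewed by the investigators on an ongoing basis in an open-label study (8.2), so the choice could be made when some outcomes are already known. What is at stake is how any p-value for PFS or CR rate in the study report should be read.

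**Working it through.** There is no figure in the plan to reproduce; section 9.1 shows only its heading in the public text. The check is a comparison of what each analysis needs with what the visible text provides.

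| Planned analysis | Needs | Visible text provides |
|---|---|---|
| Pairwise log-rank, PFS (9.9.2.1) | Two or more named groups | None named |
| Chi-square, CR rate (9.9.2.2) | Two groups, or one reference rate | Neither |
| 95% CI for CR-rate differences (9.9.2.2) | Two or more named groups | None named |
| Kaplan-Meier PFS with 95% CI (9.9.2.1) | One group | Fits the design |
| Clopper-Pearson interval for CR rate (9.7) | One group | Fits the design |

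**Could groups be formed?** Yes. Histology (FL or SLL) and umbralisib dose both vary in the population, and FLIPI is recorded at baseline (section 5, Appendix E). None is named for these tests. Section 10.5.2 also summarises laboratory abnormalities by treatment group without defining any, so undefined group wording is not confined to 9.9.2.

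**Does the choice matter?** The following is an illustration. The splits, CR rates, hazard ratio and event counts are assumptions, because the documents give none of them. All 50 subjects are assumed enrolled.

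The approximate half-width of a 95% interval for a CR-rate difference, with CR 40% in both groups, is 1.96 × √[0.4 × 0.6 × (1/n1 + 1/n2)]. Power is exact, for the two-sided 0.05 Pearson chi-square test of 30% v 50%.

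| Split | Half-width | Power |
|---|---|---|
| 25 / 25 | 1.96 × √(0.24 × 0.0800) = 27 points | 33% |
| 40 / 10 | 1.96 × √(0.24 × 0.1250) = 34 points | 23% |
| 44 / 6 | 1.96 × √(0.24 × 0.1894) = 42 points | 17% |
| 47 / 3 | 1.96 × √(0.24 × 0.3546) = 57 points | 13% |

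The last two rows use the run-in cohort sizes of 3 to 6. According to the Summary of Changes, "Two safety run-in cohorts of 3 - 6 subjects each were added at a dose of 600 mg and 800 mg umbralisib" in Version 2.0, so these rows do not describe anyone enrolled before that. The normal approximation is rough at such sizes.

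For the log-rank test, power is Φ(√[d × π(1 − π)] × ln 2 − 1.96) at hazard ratio 0.5, with d events and a share π of subjects in one group:

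- Equal split, d = 10: Φ(1.096 − 1.96) = 19%.
- Equal split, d = 30: Φ(1.898 − 1.96) = 48%.
- 88:12 split, d = 10: Φ(0.712 − 1.96) = 11%.
- 88:12 split, d = 30: Φ(1.234 − 1.96) = 23%.

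The information in these tests therefore depends heavily on which groups are meant, and the visible text does not say.

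**What the one-group analysis gives.** With 50 subjects, two-sided 95% Clopper-Pearson intervals for assumed CR counts are:

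- 10/50: 10.0% to 33.7%
- 15/50: 17.9% to 44.6%
- 20/50: 26.4% to 54.8%
- 25/50: 35.5% to 64.5%

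**The case against.** **Redaction.** A block after the secondary objectives in the synopsis is blacked out, and section 9.1 is empty in the public text. The PFS paragraph refers to a null value as if it were defined elsewhere, so groups or a reference CR rate could be too. This stands. The point is limited to the visible text, and the fix is conditional.

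**The SAP will settle it.** Section 9 says the methods may be revised, that a formal SAP will give the details before database lock, and that the study report will discuss deviations from it. This lowers the risk. But naming a test that needs two groups in a one-regimen design is more than a detail left for later, and a deadline of database lock does not require the SAP to precede knowledge of responses.

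**Blinded decisions.** Section 13.5 states the aim that clinical and statistical decisions be made blind to treatment. It blinds most sponsor staff and keeps unblinded Clinical Operations staff out of analysis discussions except on safety. This also stands as mitigation. It is not complete: the Medical Monitor is unblinded and is not named in that bar.

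**Low stakes.** The tests concern secondary endpoints, no visible decision rule depends on them, and section 9.2 is a general convention that does not make them confirmatory. All of this is right and limits the weight of the point.

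**Incomplete remedy.** Logistic models on unspecified baseline parameters (9.9.1, 9.9.2.2) would remain after the deletions, and histology is such a parameter. This is true, but those models do not presuppose a second treatment group and are a separate matter.

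A reader might go further and count the possible contrasts to obtain a false-positive rate for the plan. The documents do not support such a figure: they list no contrasts, and any list is the reader's own. Even a ceiling of 0.05 per test would not be safe. The exact size of the Pearson chi-square test with 13 subjects in each of two groups and a true CR rate of 50% is about 0.076.

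**Conclusion.** On the visible text, the pairwise log-rank test, the chi-square test and the intervals for CR-rate differences do not fit a one-regimen study without a comparator. They are wrong as written, and should be corrected or given named groups.

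The scope is two of the three secondary efficacy endpoints: PFS and CR rate. DOR has no two-group analysis, and the primary ORR estimate with its interval is untouched. The consequence is an open choice of groups for tests at two-sided 0.05, reduced but not removed by the provisions in sections 9 and 13.5. No error rate can be attached to that choice from the documents. The precision and power figures above are illustrations under stated assumptions.

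Two stronger inferences are not supported. One is that the tests cannot be run: they can, once a grouping is chosen. The other is that the sponsor has left the groups undefined everywhere: the redacted text may define them.

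**What to change.** Unless the redacted synopsis text or section 9.1 defines the groups:

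- Delete the pairwise log-rank sentence in 9.9.2.1.
- Delete the chi-square test and the wording on CR-rate differences in 9.9.2.2.
- Report the CR rate with both limits of its 95% Clopper-Pearson interval. Section 9.7 already gives the method but speaks of presenting the lower bound, while 9.9.2.2 already calls for 95% intervals.
- Keep Kaplan-Meier PFS with 95% intervals. The one-sample log-rank test is a separate matter and is not affected.

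If the redacted text does define groups, name them in both sections. If an FL v SLL contrast is wanted, name it in the SAP before outcome data are reviewed and report it as an exploratory estimate with an interval.

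The cost is wording only, in the protocol or the SAP, with no new subjects or data. The downside is that no group contrast would carry a p-value.
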